### 3.8 Pharmacokinetics

For each treatment group in the PK-evaluable population, serum concentrations of the study drug will be summarized by visit/timepoint with descriptive statistics. Individual novel agent concentrations will be summarized similarly. Serum concentrations will be reported in ug/mL, and the lower limit of quantification (LLOQ) for each analyte will be defined in the SPP. The following statistics are presented: n, n below LLOQ, geometric mean, geometric coefficient of variation (%), arithmetic mean, standard deviation, coefficient of variation (%), median, minimum, and maximum.

More details about calculations can be found in the SPP. All serum concentration data will be listed for each subject, by analyte.

## 4 INTERIM ANALYSIS

Interim analyses comparing durvalumab in combination with novel agents to durvalumab alone will be performed in a continuous manner using a joint Bayesian predictive probability. Bayesian predictive probability has been used in the setting of single-arm trials with tumor response endpoints such as OR and allows for continuous assessments for early Go/No-Go decision making ([Lee and Liu, 2008](#)). A joint Bayesian predictive probability approach

allows for continuous assessments of the delta ( $\Delta$ ), or difference, of the DCRs between durvalumab/novel agent combinations and durvalumab alone ([Pulkstenis et al., 2017](#)).

Interim analyses will begin after approximately 30 subjects in control arm (durvalumab alone) have been randomized and have reached the data cutoff criterion. The data cutoff criterion is defined as the opportunity to be followed for at least 16 weeks at the time of the data cutoff (i.e., dosed at least 16 weeks prior to the time of the data cutoff). The interim analysis will be based on the subset of the ITT Population that have satisfied the data cutoff criteria. Enrollment will not pause during the interim analysis before the decision is made.

Following this initial interim analysis, subsequent interim analyses will be performed for each experimental arm regardless of whether it starts enrollment later than control arm. Specifically, an interim analysis will be performed once each experimental arm has approximately 30 ITT subjects reach the data cutoff criterion. For interim analyses that will lead to an early No-Go decision, a response is defined as either a confirmed or unconfirmed CR or PR as per RECIST v1.1. Only concurrent control subjects, i.e., enrolled during the same period as the experimental arm, will be included in interim analyses. A comparison of each experimental arm versus all control subjects may be included as a supportive analysis.

The Target Value (TV) is set to demonstrate a 15% increase in  $\Delta$ DCR at 16 weeks, where  $\Delta$ DCR is the difference in DCR between an experimental arm and control arm. At final analysis, No-Go criteria will be met if the probability that the true  $\Delta$ DCR exceeds the prespecified TV of 15% is less than 10% (i.e., No-Go:  $P[\Delta\text{DCR} > \text{TV}] < 10\%$ ).

Given the existing observed data during the continuous monitoring stage, the joint Bayesian predictive probability is obtained by calculating the probability of reaching a No-Go decision should the treatment groups be randomized and evaluated to the maximum planned final sample size of 60. Further randomization into both treatment groups will be terminated if No-Go criteria are met.

- Early No-Go is met if it is predicted that there is a high probability of reaching a No-Go decision upon full randomization of 60 subjects given the existing observed data (i.e., predictive probability of a No-Go decision  $> 95\%$ ).

[Table 4.1](#) illustrates the sample algorithm to make an early No-Go decision based on DCR at 16 weeks at the interim analysis when control arm and an experimental arm each have 30 subjects.

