#### 4.8.3      Efficacy

The final efficacy analyses will be based on the ITT Population defined in Section 4.8.1. Response will be summarized and compared between the experimental arm and control arm. Time-to-event data will be summarized using the Kaplan-Meier estimates. The following efficacy endpoints will be analyzed. Each experimental arm will be compared to the control arm. There will be no formal comparisons between any experimental arms. RECIST v1.1 will be used as primary analysis for all endpoints when applicable. Localized post-radiation changes which affect lesion sizes may occur and there may be high levels of necrosis/fibrosis with little or no active tumor in recently irradiated lesions. However, accepting these limitations in this patient population with prior curative radiation, treatment the prior irradiated lesions may be considered measurable and selected as target lesions providing they fulfill the other criteria for measurability. More details will be provided in the statistical analysis plan.

- Best overall response (BOR), defined as the best response (in the order of complete response [CR], PR, SD, PD, and not evaluable) among all overall responses recorded from randomization until progression, or the last evaluable disease assessment in the absence of PD prior to the initiation of subsequent anticancer therapy or discontinuation from the study, whichever occurs first. The BOR of CR or PR must be confirmed, which means a response of CR/PR is recorded at 1 visit and confirmed by repeat imaging not less than 28 days (4 weeks) after the visit when the response was first observed with no evidence of progression between the initial and CR/PR confirmation visit.
- OR, defined as BOR of confirmed CR or confirmed PR according to RECIST v1.1.
- DC, defined as BOR of confirmed CR, confirmed PR, or SD based on RECIST v1.1. Disease control rate (DCR) at 16 weeks is defined as a BOR of confirmed CR, confirmed PR or having SD with duration of SD lasting 16 weeks.
- DoR, defined as the time from the first documentation of a subsequently confirmed OR to the first documentation of a disease progression according to RECIST v1.1 or death due to any cause, whichever occurs first. Only subjects who have achieved OR (confirmed CR or confirmed PR) will be evaluated for DoR.

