#### **4.8.3.2 Secondary Efficacy Analyses**

Secondary efficacy endpoints include DoR, DC, PFS, and OS. Analyses of secondary endpoints will be performed as follows.

- DoR according to RECIST v1.1 will be analyzed using the Kaplan-Meier method for those subjects with OR in the corresponding analysis populations. The median of DoR with 95% CI will be estimated based on the Kaplan-Meier curves.
- The DCR according to RECIST v1.1 is defined as the proportion of subjects with DC. The 2-sided 95% CI of DCR will be provided using an exact probability method. DCR at 16 weeks will be estimated along with the 2-sided 95% CI.
- PFS according to RECIST v1.1 will be analyzed using the Kaplan-Meier method. The median PFS with 95% CI will be estimated based on the Kaplan-Meier curves. PFS-12 will be estimated based on the Kaplan-Meier curves along with their 95% CIs when applicable. An estimate of the difference in PFS-12 between an experimental arm and the control arm will be reported. Comparison of treatment arms for PFS-12 will be performed under complementary log-log transformation of the Kaplan-Meier estimates of PFS-12 (Klein et al, 2007)
- OS will be analyzed using the Kaplan-Meier method. The median OS with 95% CI will be estimated based on the Kaplan-Meier curves. The 1-year OS rates will be estimated based on the Kaplan-Meier curves along with their 2-sided 95% CI when applicable.

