#### **4.8.7 Interim Analysis**

Interim analyses will be conducted during the course of the study to evaluate the clinical activity and safety of any experimental arm in comparison with the control arm. The results of the interim analyses may be used for internal program decision and/or potential interactions with regulatory agencies on future development. The first interim analysis will be performed once the control arm has 30 ITT subjects who have reached the data cutoff criteria (defined as the opportunity to be followed for at least 16 weeks at the time of data cutoff). The DCR at Week 16 will be used for No-Go decision, and ORR may be used for early Go decision. Enrollment will not be paused for interim analyses.

Bayesian PP will be used to evaluate clinical activity ([Lee and Liu, 2008](#)). [Table 10](#) illustrates the sample algorithm to make a No-Go decision based on DCR at 16 weeks at the interim analysis when the control arm and an experimental arm each have 30 subjects. If an early No-Go decision is made, enrollment to the corresponding experimental arm will be stopped. In

this study, we assume a target value (TV) of  $\Delta$ DCR at 16 weeks as 15%, where  $\Delta$ DCR is the difference in DCR between an experimental arm and control arm.

- An experimental arm will meet the No-Go criteria if the probability that the true  $\Delta$ DCR is larger than TV is less than 10%, ie,  $\text{Prob.}(\text{True } \Delta\text{DCR} > 0.15) < 0.10$ . A No-Go decision will be made at an interim analysis if the PP of meeting the No-Go criteria given observed data is greater than 95%, ie,  $\text{PP}[\text{Prob.}(\Delta\text{DCR} > 0.15) < 0.10] > 0.95$ .

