#### **3.4.2.1 Best Overall Response**

Best overall response (BOR) will be based on all post-baseline disease assessments that occur prior to disease progression, and/or prior to the initiation of subsequent anticancer treatment. BOR will be summarized with the number and percentage of subjects for the following categories: complete response (CR); partial response (PR); stable disease (SD); progressive disease (PD); and non-evaluable (NE). At least 7 weeks (8 weeks minus 1 week to allow for the protocol-defined disease assessment window) from randomization of IP must elapse without a subsequently radiological disease progression to assign a best overall response of SD.

Confirmation of CR and PR is required and must occur at least 4 weeks after initial documentation of CR or PR. If CR is pending confirmation and is designated at an assessment followed by 1 or more NE assessments, and/or PR assessments such that 1) the Target Lesion Response is CR and the Non-Target Lesion Response is NE, or 2) the Target Lesion Response is PR due solely to an increase in one or more lymph nodes to a size  $\geq 10$  mm and the Non-Target Lesion Response is either CR or NE, CR may be confirmed thereafter. Similarly, if a PR is pending confirmation and is designated at an assessment followed by 1 or more NE and/or SD assessments, PR may be confirmed thereafter.

In general, subjects not classifiable under the RECIST v1.1 response categories due to insufficient data or early death will be classified as NE for BOR but will be counted in the denominator of all response rate calculations. This generalization includes if a subject has missing lesion data at baseline. In this scenario, the subject will be classified as NE for BOR.

If a subject is missing lesion data at a disease assessment and yet PD criteria is met despite the missing data, the subject will be classified as PD.

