### **3.4.2.3 Disease Control**

Disease control rate (DCR) is defined as the proportion of subjects with a BOR of confirmed CR, confirmed PR, or SD (maintained for  $\geq 16$  weeks). DCR will be estimated with a 95% CI using the exact probability method. An estimate of the difference in DCR between each experimental arm and control arm will be reported and tested for significance with the Cochran–Mantel–Haenszel test.

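### The SAP analyses 16-week disease control under the name of the protocol's any-duration endpoint, and does not say which disease control rate the final No-Go criterion uses

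*SAP*

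**What the plan says.** **Protocol.** Section 4.8.3 gives two quantities. The secondary endpoint is "DC, defined as BOR of confirmed CR, confirmed PR, or SD based on RECIST v1.1", with no condition on how long the SD lasts. DCR at 16 weeks "is defined as a BOR of confirmed CR, confirmed PR or having SD with duration of SD lasting 16 weeks". Section 4.8.3.2 keeps them apart: DCR is the proportion with DC and gets an exact 95% CI, and then "DCR at 16 weeks will be estimated along with the 2-sided 95% CI". Section 4.8.7 assigns the 16-week version to futility: "The DCR at Week 16 will be used for No-Go decision, and ORR may be used for early Go decision".

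**SAP, final analysis.** Section 3.4.2 lists DC as a secondary endpoint. Section 3.4.2.3 reads "Disease control rate (DCR) is defined as the proportion of subjects with a BOR of confirmed CR, confirmed PR, or SD (maintained for", and the bracket ends with at least 16 weeks. It plans an exact CI, an arm difference and a Cochran–Mantel–Haenszel test for that quantity. Section 3.4.2.1 sets a much shorter minimum for a BOR of SD: "At least 7 weeks (8 weeks minus 1 week to allow for the protocol-defined disease assessment window", counted from randomization. Section 3.4.5 adds a confirmed/unconfirmed DCR, analysed as in section 3.4.2.

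**SAP, interim.** Section 4 applies the No-Go rule to DCR at 16 weeks and states that "a response is defined as either a confirmed or unconfirmed CR or PR as per RECIST v1.1". It gives the final No-Go criterion as a posterior probability that ΔDCR exceeds 15%, without saying which responses count. The internal Go rule in section 7.2 uses confirmed responses only.

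**The concern.** Two separate problems follow.

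1. A named secondary endpoint of the protocol would be reported as something else. A reader of the CSR who looks up DC in the protocol would take the SAP's DCR to include all stable disease, when it leaves out every SD that ended before 16 weeks.

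2. Early No-Go is a predictive probability: it takes the interim counts and asks how likely the No-Go criterion is at 60 subjects per arm. That calculation is coherent only if the interim count and the final count measure the same event. The interim event is defined more loosely than the protocol's, and the final event is not pinned down, so a reader cannot tell whether the condition is met.

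At stake are the correct reporting of a secondary endpoint and the traceability of a stopping rule. The primary endpoint, ORR, is not affected.

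**Working it through.** **Step 1. Which subjects count where.** Scans fall at Cycle 3 and Cycle 5, about weeks 8 and 16, within 7 days (Protocol Table 5). In the table, PD is taken to be documented before 16 weeks are complete.

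| Course | Protocol DC | Protocol DCR at 16 wk | SAP 3.4.2.3 | SAP 4 interim No-Go |
|---|---|---|---|---|
| Confirmed CR/PR | yes | yes | yes | yes |
| SD lasting 16 weeks or more | yes | yes | yes | yes |
| SD at week 8, then PD | yes | no | no | no |
| Unconfirmed PR at week 8, then PD | yes, if BOR falls back to SD | no | no | yes |

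SAP 3.4.2.3 agrees with the protocol's DCR at 16 weeks and not with its DC; row 3 is the difference. Row 4 is the interim difference. At the final analysis a row 4 subject fails under SAP 3.4.2.3 and succeeds under the unconfirmed version in SAP 3.4.5. An unconfirmed responder who stays progression-free for 16 weeks would plausibly count as SD anyway. No window is stated for the 16 weeks, so subjects first responding or progressing at a scan near that date are also uncertain.

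**Step 2. Size of the DC difference.** Input: median PFS 17.2 months on durvalumab (Protocol 1.1). Assumption: exponential PFS, S(t) = 0.5^(t/17.2), with t in months.

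- 7 weeks = 49/30.4375 = 1.610 months, S = 0.937
- 8 weeks = 56/30.4375 = 1.840 months, S = 0.929
- 16 weeks = 3.680 months, S = 0.862

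The gap is 6.6 points from week 8 and 7.5 points from week 7, so about 7 points, or roughly 4 of 60 subjects (0.07 × 60 = 4.2). The SAP's benchmark control DCR is 60% (Table 4.2). If that were read as the progression-free share at 16 weeks on an exponential curve, S(8 weeks) = √0.60 = 0.775 and the gap would be 17.5 points. That overstates it, because DCR also loses subjects who are not evaluable.

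**Step 3. Reproducing the No-Go rule.** Inputs: TV 15%, final threshold 10%, predictive threshold 95%, 30 per arm at interim and 60 at final, control DCR 60% (SAP section 4). No prior is stated; Beta(1,1) is assumed. Final No-Go is P(pE − pC > 0.15) < 0.10 at 60 per arm. Early No-Go is a beta-binomial predictive probability of that event above 0.95, with one look.

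| True δ | All No-Go, SAP | recomputed | Early No-Go, SAP | recomputed |
|---|---|---|---|---|
| 0% | 68% | 68.4% | 19% | 19.0% |
| 5% | 46% | 46.9% | 11% | 10.5% |
| 10% | 25% | 25.9% | 5% | 5.1% |
| 15% | 11% | 11.0% | 2% | 2.1% |
| 20% | 3% | 3.5% | 1% | 0.7% |
| 25% | 1% | 0.7% | 0 | 0.2% |

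Table 4.1 matches in 20 of 21 rows. Control 28 is the exception (stated ≤28, computed ≤27), and a Beta(0.5,0.5) prior reproduces that row. The arithmetic of the rule is therefore sound; the open question is which subjects enter it.

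**Step 4. Sensitivity of the No-Go rule.** With 18/30 controlled in the control arm, 14/30 in the experimental arm gives a predictive probability of 0.973 (No-Go) and 15/30 gives 0.941 (continue). The documents do not give the share of subjects who count only under the interim definition, so a range is assumed. Probability of early No-Go:

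| Extra share | δ=0: both arms | δ=0: exp. only | δ=0: control only | δ=15%: both | δ=15%: exp. only | δ=15%: control only |
|---|---|---|---|---|---|---|
| 0 | 0.190 | 0.190 | 0.190 | 0.021 | 0.021 | 0.021 |
| 1/30 | 0.198 | 0.129 | 0.274 | 0.022 | 0.011 | 0.041 |
| 2/30 | 0.211 | 0.084 | 0.377 | 0.023 | 0.005 | 0.075 |
| 10 points | 0.227 | 0.051 | 0.494 | 0.024 | 0.002 | 0.128 |

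An equal shift barely matters. An unequal one does.

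**The case against.** Several points on the other side stand.

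- **DC can be recovered.** SAP 3.4.2.1 tabulates BOR by category, and protocol DC is the sum of CR, PR and SD. A reader might infer that the endpoint is lost altogether. It is not: what is missing is a labelled rate with its CI and arm comparison.
- **The final No-Go definition is open, not contradictory.** A reader might infer that the rule predicts a confirmed-only final count from an unconfirmed interim count. The documents do not say so. SAP section 4 is silent, and SAP 3.4.5 supplies a final DCR that would match the interim count.
- **Different counts for DC and No-Go are partly by design.** The protocol itself gives No-Go the 16-week version, so a difference between the secondary endpoint and the stopping measure is not in itself an error.
- **The 7 points say nothing about No-Go.** Both No-Go readings use 16-week disease control, so that figure concerns only the reported DC endpoint.
- **A lenient No-Go count can be defended.** A response first seen at week 16 cannot yet be confirmed at a 16-week cutoff, and a strict Go rule beside a lenient No-Go rule is coherent. The SAP gives no reason for the choice, but confirmed-only is not the only acceptable answer.
- **Timing.** The SAP version history refers to a completed first interim, and Protocol Amendment 4 says all subjects have finished treatment. New wording cannot change those enrolment decisions.

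These points limit the size of the problem. They do not reconcile SAP 3.4.2.3 with the protocol's DC, or say which DCR the final criterion uses.

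**Conclusion.** The point holds in two parts.

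First, SAP 3.4.2.3 is wrong as written for the endpoint it names: it analyses the protocol's DCR at 16 weeks in place of DC. The expected gap is about 7 points under an exponential curve with a 17.2-month median. That curve is an assumption, and the effect on the arm difference is unknown.

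Second, the No-Go count departs from the protocol's confirmed-only definition without explanation, and the final criterion it predicts is not specified. Few subjects are likely to be affected, mainly those with an unconfirmed response near week 8 and progression by week 16. The effect on the rule is small if the arms are affected alike (0.190 to 0.227 at δ = 0 with an assumed 10-point shift). It is material only if one arm is affected more, for which the documents give no evidence.

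Nothing in the documents shows that any interim decision was wrong.

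**What to change.** In the SAP:

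1. Report DC (any SD) and DCR at 16 weeks as two separately named endpoints, each with an exact CI and an arm difference.
2. State one definition of DCR at 16 weeks for the interim count, the predictive probability and the final No-Go criterion. Reconcile it with Protocol 4.8.3 and 4.8.7, and show the other version as supportive.

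For interims already done, state in the CSR which definition was used and whether the No-Go result is the same under the other.

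The cost is SAP wording and one or two table rows. No new data are needed.

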### **4.6 Treatment Assignment and Blinding**

#### **4.6.1 Methods for Assigning Treatment Groups**

Once confirmed that the subject meets eligibility criteria, an IXRS will randomize the subject to a treatment arm according to the randomization scheme.

A randomization method with dynamically changing randomization ratios will be employed to account for fluctuation in the number of treatment arms open for enrollment over the course of the study. Randomization will be stratified by histology (adenocarcinoma vs non-adenocarcinoma). The randomization scheme will use an equal ratio to all study treatment arms open for enrollment (eg, if experimental arms are opened sequentially, an experimental arm is added/closed, or enrollment in an experimental arm is suspended). Additionally, the following considerations regarding randomization will apply:

- If there is no experimental arm open for enrollment, then enrollment will be paused. Any subject who had consented previously and was in screening when the experimental arm(s) was closed due to safety concerns may be allowed to enter into the study but must be allocated to the control arm.
- Once the control arm enrolls 60 subjects, a subsequent randomization scheme may be initiated to optimize the number of subjects allocated to control arm.
- At any point during the study, the control arm will have no less than a 33% chance to be randomized in comparison to the active experimental arm that has the lowest randomization ratio in the study.

Study treatment must be administered within 3 days after the treatment arm is assigned. If there is a delay in the administration of study treatment such that it will not be administered within the specified timeframe, the study monitor must be notified immediately.

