## 2.2 Study Design

COAST is a Phase 2, open-label, multicenter, randomized, multidrug platform study of durvalumab alone or in combination with novel agents in subjects with locally advanced, unresectable, Stage III NSCLC.

The study will evaluate the clinical activity and safety of durvalumab alone or in combination with novel agents in subjects with Stage III NSCLC who have not progressed following definitive concurrent chemoradiotherapy (cCRT) (Figure 1 in protocol). Subjects will be

randomized into the study and initiate study treatment within 42 days from the last session of cCRT. Up to approximately 80 sites globally will participate in this study.

Subjects may be treated for up to 12 months. Study treatment will be discontinued upon confirmed disease progression, unacceptable toxicity, or other reasons, e.g., subject decision or noncompliance with study procedures. Overall, all subjects continuing in the study must adhere to the study procedures for up to 5 years (from randomization) provided they achieve disease control (DC) and remain disease free.

After completing the 5-year post-randomization study period, all subjects included into any treatment arm may be contacted annually for survival until 5 years after the final subject is randomized into the study or until the sponsor stops the study, whichever occurs first. The platform nature of the study allows an experimental arm to be permanently closed while the overall COAST study remains open.

New durvalumab combination experimental arms may be added based on emerging non-clinical and clinical data via protocol amendment. Interim futility analyses will be performed using Bayesian predictive probability.

Details about treatment regimen can be found in Section 3.1.2 of the protocol.

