## 2.3 Treatment Assignment and Blinding

### Treatment Assignment

An interactive voice/web response system (IxRS) will be used to assign investigational product (IP) kit numbers to each subject who meets the eligibility criteria. A randomization method with dynamically changing randomization ratios will be employed to account for fluctuation in the number of treatment arms open for enrollment over the course of the study. The randomization will be stratified by histology (adenocarcinoma vs non-adenocarcinoma) and will use an equal ratio to all study treatment arms open for enrollment (e.g., if experimental arms are opened sequentially, an experimental arm is added/closed, or enrollment in an experimental arm is suspended). Additionally, the following considerations regarding randomization will apply:

- If there is no experimental arm open for enrollment, then enrollment will be paused. Any subject who had consented previously and was in screening when the experimental arm(s) was closed due to safety concerns may be allowed to enter into the study but must be allocated to the control arm.

- Once the control arm enrolls 60 subjects, a subsequent randomization scheme may be initiated to optimize the number of subjects allocated to control arm.
- At any point during the study, the control arm will have no less than a 33% chance to be randomized in comparison to the active experimental arm that has the lowest randomization ratio in the study.

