### **2.4 Sample Size**

Sixty subjects will be enrolled in each of the combination therapy experimental arms and more than 60 subjects will be enrolled in the durvalumab control arm dependent upon the length of the study. The sample size of 60 subjects per experimental arm is not designed to make explicit power and Type I error considerations for a hypothesis test. It is primarily chosen to obtain a preliminary assessment of antitumor activity with a certain degree of precision.

Table 2.4-1 shows estimated differences in objective response rate (ORR) between an experimental arm and control arm along with 2-sided 95% exact CIs with a sample size of 60 subjects each. Sixty subjects per treatment arm provides a 95% CI with reasonable width (approximately  $\pm 18\%$ ) for the estimated ORR difference between a durvalumab combination experimental arm and the durvalumab control arm. For a 20% increase in ORR in any durvalumab combination experimental arm over durvalumab control arm (50% vs 30%, respectively), the lower limit of the 95% CI for the difference between these arms is 1%, which is greater than 0%, suggesting that the durvalumab combination experimental arm will have a higher ORR than the durvalumab control arm with 95% confidence.

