## **3.4 Efficacy Analyses**

### **3.4.1 Primary Efficacy Endpoint(s) and Analyses**

#### **3.4.1.1 Primary Efficacy Endpoint(s) and Analysis**

The primary efficacy endpoint is objective response (OR) per Response Evaluation Criteria in Solid Tumors version 1.1 (RECIST v1.1). ORR is defined as the proportion of subjects with a best overall response of confirmed CR or confirmed PR that occur prior to disease progression, and/or prior to the initiation of subsequent anticancer treatment. Confirmation of response requirements are defined in [Section 3.4.2.1](#) for best overall response. The primary analysis of ORR will be based on the ITT population. An estimate of the difference in ORR as well as its 2-sided 95% exact CI between each experimental arm and control arm will be reported. The rates between each experimental arm and control arm will be tested for significance with a Cochran–Mantel–Haenszel test, stratified by histology (adenocarcinoma or non-adenocarcinoma). Subjects that have missing overall response assessments will be considered as non-responders, and will therefore be counted in the denominator, but not in the numerator of ORR. Primary efficacy analysis will include control subjects that are concurrently enrolled with each experimental arm.

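### The SAP's No-Go rule closes the shared control arm as well as the failing experimental arm, which contradicts the protocol and the SAP's own randomization rules

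*SAP*

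**What the plan says.** SAP section 4 sets up the interim analysis as a comparison of one durvalumab combination with durvalumab alone. It then gives the consequence of a No-Go: "Further randomization into both treatment groups will be terminated if No-Go criteria are met".

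Other sections say or imply something different:

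- Protocol 4.8.7, on the same decision: "If an early No-Go decision is made, enrollment to the corresponding experimental arm will be stopped". The note under protocol Figure 1 likewise speaks only of stopping combination experimental arms.
- Protocol 4.6.1 and SAP 2.3 use an equal ratio across all arms open for enrollment, and name the closing of an experimental arm as one occasion for this. They add a floor: "At any point during the study, the control arm will have no less than a 33% chance to be randomized". The sentence goes on to make the floor relative to the active experimental arm with the lowest ratio, so it is not an absolute one-third.
- The same two sections give the situation in which control stops too: "If there is no experimental arm open for enrollment, then enrollment will be paused".
- SAP 2.2: "The platform nature of the study allows an experimental arm to be permanently closed while the overall COAST study remains open".
- SAP 2.4 expects that "more than 60 subjects will be enrolled in the durvalumab control arm dependent upon the length of the study".

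Who counts as a control depends on when control was open. SAP 3.4.1.1: "Primary efficacy analysis will include control subjects that are concurrently enrolled with each experimental arm". SAP 3.4.2 applies the same restriction to the secondary comparisons, and section 4 to the interim looks: "Only concurrent control subjects, i.e., enrolled during the same period as the experimental arm, will be included in interim analyses".

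**The concern.** The SAP sentence is written for a two-arm trial, where stopping for futility ends the whole trial. Here the second group is the control that all experimental arms share. Arms A and B are the initial arms and the protocol allows them to be open in parallel. Read literally, a No-Go for Arm A would close the control that Arm B is still being randomized against.

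Arm B's subjects already enrolled would keep their concurrent controls; those enrolled afterwards would have none. The primary, secondary and interim comparisons are all restricted to concurrent controls, so the comparison for the surviving arm would lose precision and part of its randomized basis.

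**Working it through.** **Reading the rules together.** Take a No-Go for Arm A.

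| Situation | SAP section 4 | Protocol 4.8.7, 4.6.1 and SAP 2.3 |
|---|---|---|
| A is the only open arm | A and control stop | A stops; no experimental arm is open, so enrollment pauses, control included |
| B is still enrolling | A and control stop | A stops; B and control continue at an equal ratio, with the floor for control |

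The texts agree in effect in the first row and conflict in the second. This step needs no arithmetic. The rest gives the size of the problem if the SAP sentence were followed in the second row.

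**How often the second row could arise.** Inputs: the No-Go boundaries in SAP Table 4.1 (30 per arm) and the 60% benchmark control disease control rate (DCR) in Table 4.2. With control count C ~ Bin(30, 0.60), experimental count E ~ Bin(30, 0.60 + δ) and boundary t(C), the early No-Go probability is P(E ≤ t(C)).

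| True δ | Calculated | Table 4.2 |
|---|---|---|
| 0% | 19.0% | 19% |
| 5% | 10.5% | 11% |
| 10% | 5.1% | 5% |
| 15% | 2.1% | 2% |

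The plan's own figures are reproduced to within rounding. Now let A and B share the same 30 controls and be looked at together (an assumption). P(A stops, B continues) is the sum over c of P(C = c) × P(E_A ≤ t(c)) × [1 − P(E_B ≤ t(c))]:

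| True δ in A | True δ in B | P(A stops, B continues) |
|---|---|---|
| 0% | 15% | 17.3% |
| 5% | 15% | 9.1% |
| 10% | 15% | 4.2% |
| 0% | 0% | 10.1% |

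**How many controls there would be.** The documents do not give this number. The first look needs 30 controls with the opportunity for 16 weeks of follow-up, and enrollment does not pause. At r controls per week, at least min(60, 30 + 16r) are randomized by then, ignoring the time from data cutoff to decision. The rates are assumptions:

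- r = 0.5: 30 + 8 = 38
- r = 1.0: 30 + 16 = 46
- r = 1.25: 30 + 20 = 50
- r = 1.875: 30 + 30 = 60, so at this rate or faster control already has 60

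**Effect on the primary comparison.** Protocol Table 9 (SAP Table 2.4-1) gives exact 95% intervals for the difference in objective response rate (ORR). An exact unconditional interval, based on the unstandardized difference with two one-sided 2.5% tests maximized over the nuisance rate, reproduces all four rows:

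| Responders, 60 per arm | Calculated | Table 9 |
|---|---|---|
| 24 vs 18 | (-8.7%, 28.2%) | (-9%, 28%) |
| 27 vs 18 | (-3.7%, 32.9%) | (-4%, 33%) |
| 30 vs 18 | (1.3%, 37.7%) | (1%, 38%) |
| 33 vs 18 | (6.4%, 42.3%) | (6%, 42%) |

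The same method with 30/60 responders in the experimental arm and 30% in a smaller control arm gives:

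| Controls | 95% CI | Half-width (points) |
|---|---|---|
| 60 (18 responders) | (1.3%, 37.7%) | 18.2 |
| 50 (15) | (1.1%, 37.9%) | 18.4 |
| 40 (12) | (-0.4%, 39.2%) | 19.8 |
| 30 (9) | (-2.7%, 41.4%) | about 22 |

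The 30-control row is a lower bound that would be exceeded in practice. The table keeps all 60 experimental subjects and assumes the arms opened together with control. An arm that opened later would have fewer concurrent controls.

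**The case against.** The strongest reply is that the sentence cannot do harm. The protocol governs randomization and is clear, and SAP 2.3 repeats its rules correctly. The wording looks like two-arm text carried into a platform study. Treatment is complete according to the Amendment 4 summary, and the SAP's last two versions serve the final study report. Tables 4.1 and 4.2 compare one arm with control and stand under either wording. This is fair, and it is why the point is a conflict to reconcile and not a predicted loss of controls.

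Several narrower points also stand. No passage says in so many words that control stays open after a No-Go; that follows from the equal-ratio rule and the control floor. SAP 2.2 does not mention control, and SAP 2.4 concerns the expected total, so both are only supporting evidence. The pause rule is not worded as the sole reason for stopping control, and protocol 4.4 lets the sponsor suspend or end any component, including after a futility analysis. That is a discretionary right, separate from the No-Go rule. The accrual rates and the simultaneous looks are assumptions; section 4 also allows later looks timed by each experimental arm. At 50 controls the loss of precision is slight. Nothing in the documents shows that any No-Go occurred.

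None of this removes the contradiction. The SAP states a stopping rule for control that its own section 2.3 and the protocol do not allow while another arm is enrolling.

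**Conclusion.** The concern holds. SAP section 4 conflicts with protocol 4.8.7 and 4.6.1 and with SAP 2.3 whenever a second experimental arm is open, and agrees with them in effect otherwise. This rests on the text alone.

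The size is conditional. Under the assumptions above, one arm stopping early while another with a true 15-point DCR gain continues has a chance of 4.2% to 17.3%, depending on the failing arm's true effect. If control then closed, the plan's own example of a 20-point ORR gain would no longer exclude zero at 40 controls, would barely change at 50, and would be unaffected if control had already reached 60.

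With treatment finished, what remains open is which rule was applied if a No-Go occurred, and whether the concurrent-control sets match it. The sentence should be corrected, but the documents give no evidence that conduct went wrong.

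**What to change.** Replace the SAP section 4 sentence with wording such as: *When an experimental arm meets the No-Go criteria, randomization to that arm ends. The control arm continues to be randomized for as long as at least one other experimental arm is enrolling, under the allocation rules of Section 2.3.*

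Add one sentence, in the SAP or the study report, stating whether any interim analysis gave a No-Go and, if so, which rule was applied to control. It should also confirm that the concurrent-control sets used under 3.4.1.1, 3.4.2 and section 4 were defined accordingly. If no No-Go occurred, it need only say so.

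The cost is one sentence replaced and one added. Study conduct and Tables 4.1 and 4.2 do not change.
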